Nicotine and carbonyls such as acrolein have well-established effects on the endothelium, suggesting that e-cigarettes may cause acute pulmonary microvascular changes. E-cigarette vapor with and without nicotine causes endothelial barrier dysfunction *in vitro* and, in humans, has been associated with decreased exhaled nitric oxide, a major vasodilator and regulator of pulmonary microvascular tone. E-cigarette-related endothelial dysfunction may therefore decrease pulmonary microvascular perfusion, which is implicated in the pathogenesis of emphysema. Until recently, direct measures of pulmonary microvascular blood flow were lacking. **Our group has developed an innovative measure of pulmonary microvascular blood flow (PMBF) on gadolinium (Gd)-enhanced magnetic resonance imaging (MRI), which we found to be markedly abnormal in early chronic obstructive pulmonary disease (COPD) and emphysema, and associated with increased endothelial microparticles, a marker of endothelial apoptosis;** however, PMBF has never been used to assess e-cigarette effects.

[figure not shown]
We therefore propose **to test the acute effects of a standardized e-cigarette exposure on pulmonary ventilation and perfusion in a randomized crossover design in 10 young, healthy, e-cigarette users.** We hypothesize that e-cigarette exposure will:

1. Increase global and regional ventilation defects on ³He-MRI.
2. Decrease global and regional pulmonary microvascular blood flow.

This pilot work will provide **the experience and data to support subsequent funding applications powered to establish definitively the acute pulmonary effects of e-cigarette vapor** of various compositions (e.g., with and without nicotine, with and without flavoring) in persons with and without chronic lung diseases (e.g., asthma and COPD) with respect to ventilation and microvascular perfusion. Furthermore, **confirmation of our hypotheses in this modest sample would provide important, vivid preliminary data to inform regulatory decisions** regarding warning labels and public health education.

2. Study Design and Statistical Procedures.

We propose a randomized crossover clinical trial following a run-in period to test the acute pulmonary effects of a standardized e-cigarette exposure on ³He-MRI/MRA measures among ten young, healthy intermittent e-cigarette users.

Pre-Screening

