Consistent with prior literature, the study e-cigarette exposure will be 10 puffs with 30-second inter-puff intervals, as directly observed by a trained research assistant, using the standardized e-cigarette. This is anticipated to generate a plasma nicotine concentration of 19 ng/mL, similar to 10 puffs of a conventional cigarette. The exposure will be administered under a fume hood (Airtech Laminar Flow Workstation, Model ATG 220 UV Therapy Isolation Booth, <http://www.airtechlaminarflow.com/atg-220.htm>) at the enrollment visit in the CTSA and in the negative-pressure MRI scanner rooms at two of the four imaging visits.

Blinding

The "unexposed" condition will be breathing from the study e-cigarette with the battery off (or, if this is not feasible, completing the prescribed "puff" maneuvers using only room air). To assess the adequacy of blinding, participants will be interviewed at the end of study regarding whether they were able to guess correctly their allocation assignments.

Imaging

Gadolinium-enhanced MRI will be performed on days 2 and 6, ensuring >48-hour clearance of gadolinium, and ³He-MRI for ventilation will be performed on days 3 and 7.

Statistics

As this is a randomized crossover trial, statistical procedures will consist mainly of permutation tests. The proposed study is designed to generate preliminary data rather than definitively to confirm or rule out acute pulmonary toxicities of e-cigarettes, although the proposed sample may be adequate to detect large effects (**Table 1**). We will have 60% power at an alpha of 5% in two-tailed significance testing to detect the 1.02 increase in ventilation defect percentage (VDP) that may be predicted based on prior literature showing an approximately 3% FEV₁ decline with e-cigarettes and additionally assuming that prior associations between FEV₁ and VDP are linear. Based on published associations between secondhand smoke, endothelial microparticle concentrations, and pulmonary microvascular measures such as signal intensity (SI) we might anticipate a 5% decrement in PMBF from secondhand smoke exposure alone; however, the effect is likely to be larger for e-cigarette vapor given its much higher nicotine yield.

ΔFEV_1	ΔVDP	80%	90%	95%
1%	0.34	66	88	108
2%	0.68	24	32	39
3%	1.02	15	20	24
5%	1.70	10	12	15
ΔSI	80%	90%	95%	
-.05	189	252	311	
-.10	47	63	77	
-.15	22	28	34	
-.20	13	17	20	

3. Study Procedures

Pre-screening

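### Does the statement that 10 participants may suffice for large effects mislead about the perfusion hypothesis?

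*Combined protocol and SAP*

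**What the plan says.** Section 1 (Study Purpose and Rationale) describes a "randomized crossover design in 10 young, healthy, e-cigarette users" with two numbered hypotheses: more ventilation defects, and lower pulmonary microvascular blood flow (PMBF). It adds that "confirmation of our hypotheses in this modest sample would provide important, vivid preliminary data to inform regulatory decisions".

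Section 2 (Statistics) sets the aim: "The proposed study is designed to generate preliminary data rather than definitively to confirm or rule out acute pulmonary toxicities of e-cigarettes". The same sentence continues "although the proposed sample may be adequate to detect large effects" and cites Table 1. The method is stated as "statistical procedures will consist mainly of permutation tests". Power with 10 participants is given once: 60% at two-sided 5% for a VDP increase of 1.02. For perfusion the text says "we might anticipate a 5% decrement in PMBF from secondhand smoke exposure alone" and then "the effect is likely to be larger for e-cigarette vapor given its much higher nicotine yield". It gives no perfusion power at 10 participants.

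Table 1 lists sample sizes for 80%, 90% and 95% power:

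| Effect | 80% | 90% | 95% |
|---|---|---|---|
| ΔVDP 0.34 | 66 | 88 | 108 |
| ΔVDP 0.68 | 24 | 32 | 39 |
| ΔVDP 1.02 | 15 | 20 | 24 |
| ΔVDP 1.70 | 10 | 12 | 15 |
| ΔSI -.05 | 189 | 252 | 311 |
| ΔSI -.10 | 47 | 63 | 77 |
| ΔSI -.15 | 22 | 28 | 34 |
| ΔSI -.20 | 13 | 17 | 20 |

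**The concern.** The adequacy remark cites a table in which only one of 24 entries is 10 or below (ΔVDP 1.70 at 80% power), and none of those is for perfusion. Power with 10 participants is disclosed for VDP only, so a reader could assume that the remark covers the second hypothesis too. The perfusion block is also in SI, while the hypothesis and the 5% figure are stated for PMBF.

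If 5% were the true effect, the perfusion comparison would have very little power. A null result would say almost nothing, and a significant one would tend to overstate the effect. Section 1 says the pilot should support later, properly powered funding applications and might inform regulators, so a later study planned on such an estimate could be too small.

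**Working it through.** **Inputs.** n = 10, two-sided α = 0.05, and Table 1 as above. The plan gives no SD, so it has to be back-solved. A paired t-test stands in for the planned permutation test. Write Δ for the mean paired difference and SD for the standard deviation of the paired differences. Power is the probability that a noncentral t with 9 degrees of freedom and noncentrality √10 × Δ/SD falls outside ±2.262.

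**The plan's own figure.** For ΔVDP 1.02, a standardized effect Δ/SD = 0.785 returns sample sizes of 15, 20 and 24, exactly as tabulated. Power at n = 10 is then 60.0%. The stated 60% is reproduced.

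**SD implied by the ΔSI rows.** Under the paired t-test, an SD between about 0.230 and 0.244, differing by row, returns all three cells of each row. No single value fits every row exactly. A normal approximation with SD 0.245 comes within about one participant of every cell. The range 0.225 to 0.244 is used below to be safe.

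**Power at n = 10.** For example, at Δ = .05 and SD 0.244 the noncentrality is 3.162 × .05/0.244 = 0.648 and power is 9.0%. At Δ = .20 and SD 0.225 it is 3.162 × .20/0.225 = 2.811 and power is 70.7%.

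| ΔSI | SD 0.225 | SD 0.236 | SD 0.244 |
|---|---|---|---|
| -.05 | 9.7% | 9.2% | 9.0% |
| -.10 | 24.2% | 22.4% | 21.3% |
| -.15 | 46.9% | 43.5% | 41.2% |
| -.20 | 70.7% | 66.6% | 63.7% |

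Power of 80% needs Δ/SD = 0.996, that is Δ = 0.996 × 0.225 = .224 up to 0.996 × 0.244 = .243. A simulated sign-flip permutation test gives about 8.5% at -.05, so the choice of test does not drive the result.

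**What a significant result would look like.** The value 2.262 × SD/√10, which is 0.161 to 0.175 over the SD range, might be taken as the smallest mean difference that can be significant. It is not, because each trial estimates its own SD. In 200,000 simulated trials with SD 0.24 and a true effect of .05, about 41% of significant results had an absolute mean difference below 0.16. Average exaggeration among significant results is about 3.4-fold at a true effect of .05, 1.9-fold at .10, 1.4-fold at .15 and 1.2-fold at .20.

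**The sentence against the table.** The remark concerns large effects. In the VDP block the largest effect, 1.70, needs exactly 10 at 80% power. In the SI block the largest effect, -.20, has 64 to 71% power with 10, no lower than the 60% that the plan openly reports for its VDP scenario. The -.05 row is the smallest perfusion effect listed and cannot test a claim about large ones.

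**The case for a change.** The best case for a change is that pilot status excuses low power but not an adequacy remark that its own table fails to support at 80% power for one of two hypotheses. The 5% benchmark is the only perfusion effect with a number attached. Doubling it to 10% gives power of only 21 to 24%, tripling it gives 41 to 47%, and 80% requires nearly five times the benchmark. The cure would be a sentence or two, with no added participants.

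The table reading stands: no tabulated SI effect reaches 80% power with 10 participants, and the text does not say so. It is also true that the plan never says how ΔSI maps to PMBF. Neither point shows an error. The plan states no perfusion power that it then fails to deliver, and anyone following the reference to Table 1 sees 189 at -.05 and 13 at -.20. The feared misuse is not in the plan either: nowhere does it say that a significant point estimate will size the next study, and it already says that the study cannot rule toxicity in or out. Writing specific perfusion powers into the protocol would rest on a back-solved SD and on equating ΔSI with a percentage change in PMBF, which the documents do not establish.

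**Conclusion.** No change is needed. For perfusion, 10 participants give about 9% power at the secondhand-smoke benchmark, 64 to 71% at the largest tabulated effect, and 80% only near ΔSI .22 to .24. These figures assume a paired t-test, an SD of paired differences of 0.225 to 0.244 inferred from Table 1, and, for the benchmark, that ΔSI -.05 stands for a 5% fall in PMBF. They describe a small pilot whose limits the plan declares. The adequacy remark is hedged, confined to large effects and supported for ΔVDP 1.70; the 9% figure belongs to an effect smaller than the one the plan expects from e-cigarettes.

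What remains is a gap that analysts fill as routine: report the mean paired PMBF difference with its 95% confidence interval and the SD of the differences, and say how SI relates to PMBF. A clearer sentence on perfusion power would be a courtesy to readers. It would change neither the design, the analysis nor any conclusion the trial can draw.

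### Does the 60% power claim for VDP contradict Table 1 because the VDP rows imply different standard deviations?

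*Combined protocol and SAP*

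**What the plan says.** The study is a pilot, "in a randomized crossover design in 10 young, healthy, e-cigarette users" (section 1). Section 2, Statistics, describes the analysis in one line: "As this is a randomized crossover trial, statistical procedures will consist mainly of permutation tests". It then states the power: "We will have 60% power at an alpha of 5% in two-tailed significance testing to detect the 1.02 increase in ventilation defect percentage (VDP"). The 1.02 comes from an FEV₁ decline of about 3%, "additionally assuming that prior associations between FEV₁ and VDP are linear".

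Table 1 lists numbers of participants for 80, 90 and 95% power. For VDP increases of 0.34, 0.68, 1.02 and 1.70 these are 66/88/108, 24/32/39, 15/20/24 and 10/12/15. For SI decrements of 0.05, 0.10, 0.15 and 0.20 they are 189/252/311, 47/63/77, 22/28/34 and 13/17/20. The text gives no SD, within-person correlation or variance model for either block. On purpose, the same paragraph says: "The proposed study is designed to generate preliminary data rather than definitively to confirm or rule out acute pulmonary toxicities of e-cigarettes".

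**The concern.** With one fixed SD, the required number falls roughly with the square of the effect. From 0.34 to 1.02 the effect triples, so the number should fall about ninefold. Table 1 goes from 66 to 15, a factor of 4.4. The SI block seems to obey the rule: doubling the decrement from 0.05 to 0.10 takes 189 to 47, a factor of 4.0. It is natural to conclude that the VDP block was miscalculated and that the 60% depends on which row's SD one believes.

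If so, the only power figure stated in the text would be unreliable, and the small-effect rows could mislead the later applications for which the pilot is meant to provide "the experience and data to support subsequent funding applications powered to establish definitively the acute pulmonary effects of e-cigarette vapor". With the SD behind the 60% held constant, the 0.34 row would need 117 participants for 80% power, not 66.

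**Working it through.** **Inputs.** Two-sided α = 0.05, n = 10 and effect 1.02 (sections 1 and 2), and the 24 cells of Table 1. The SD of the paired difference is not stated and is back-solved. A paired t-test stands in for the planned permutation test.

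**Formula.** Power = P(T > t₀.₉₇₅,ₙ₋₁), where T is noncentral t with n − 1 degrees of freedom and noncentrality λ = (δ/SD)·√n. The required N is the smallest n that reaches the target power.

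**Step 1: the plan's own figure.** The SDs that return 15, 20 and 24 for δ = 1.02 run from 1.297 to 1.311. With SD = 1.30 and n = 10, λ = (1.02/1.30) × √10 = 2.48 against a critical value of 2.262, and power is 60.0%. With SD = 1.31 it is 59.3%. The stated 60% therefore follows from the Table 1 row for the same effect.

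**Step 2: every row.** SDs that return all three cells of a row exactly:

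| VDP effect | SD | SI decrement | SD |
|---|---|---|---|
| 0.34 | 0.968–0.971 | 0.05 | 0.2435–0.2438 |
| 0.68 | 1.133–1.138 | 0.10 | 0.2390–0.2395 |
| 1.02 | 1.297–1.311 | 0.15 | 0.233–0.235 |
| 1.70 | 1.629–1.651 | 0.20 | 0.2305–0.235 |

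The VDP intervals do not overlap, so that part of the observation is correct. But the first three SI intervals do not overlap either. A constant SI SD of 0.242 gives 186/249/307, 48/64/79, 23/30/36 and 14/18/22: close, but not one of the 12 cells matches. The best constant SD matches 6 of 12. Setting the SD at 0.244 to recover 189 gives 49, 23 and 14 at 80% power for the other rows, where the table has 47, 22 and 13.

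**Step 3: is there a coherent rule?** Suppose each condition's SD is proportional to its mean (coefficient of variation c) and the two conditions have correlation r. Then

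SD of difference = c·√(m₁² + m₂² − 2·r·m₁·m₂).

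- SI, with m₁ = 1, m₂ = 1 − decrement, c = 0.322, r = 0.7: SDs 0.2436, 0.2388, 0.2350 and 0.2322, giving 189/252/311, 47/62/77, 22/28/34 and 13/17/20. Eleven of 12 cells are exact and the other is off by 1.
- VDP, with m₁ = 1.6, m₂ = 1.6 + effect, c = 0.69, r = 0.7: SDs 0.970, 1.124, 1.301 and 1.698, giving 66/88/108, 24/31/38, 15/20/24 and 10/13/16. Eight of 12 are exact and the rest are off by 1.

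A simpler line for VDP alone, SD = 0.80 + 0.5 × effect (0.97, 1.14, 1.31, 1.65), returns 11 of 12 cells, with 25 against 24 in the other. It gives 59.3% power at n = 10 for 1.02. The values of c, r and baseline are fitted, not taken from the plan.

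**Step 4: the apparent spread in power.** At n = 10 and effect 1.02, the first row's SD (0.97) gives 84% power and the last row's (1.65) gives 42%. A figure of 40% needs SD = 1.70, outside the last row's interval. These figures pair the effect 1.02 with SDs that belong to other effects. If the SD changes with the effect, power at 1.02 is about 59 to 60%, not a range.

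**The case for a change.** The strongest case for the concern is that a table of N by effect size is normally read as a constant-SD table, and the text does not say this one is different. On that reading, SD = 1.30 gives 96% power at n = 10 for 1.70, where the table lists 10 participants for 80%. It also turns the 80% column into 117, 31, 15 and 7 instead of 66, 24, 15 and 10. The linearity that the plan assumes between FEV₁ and VDP concerns the effect, not its spread. The rule that reconciles the rows is inferred.

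Three things stand: the VDP rows rest on different SDs, neither the SDs nor their source appears in the text, and the small-effect rows depend on that choice. Against this, the caption and any notes to Table 1 are not visible in the text available here, so a statement of the SD may exist.

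The step from there to a contradiction does not stand. It needs a common SD, which the plan never claims. The main support for that premise, that the SI block uses one, fails on the same exact-cell test. Recomputing the VDP rows with one SD to match SI would therefore impose a rule that neither block follows.

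**Conclusion.** The concern does not hold. The 60% and the row for the same effect agree (SD 1.30 to 1.31, power 59 to 60% at n = 10). The other VDP rows are consistent with an SD that grows with the effect, and the SI rows with an SD that shrinks as the mean falls. Both patterns fit a variance tied to the mean, so the table gives no evidence of an arithmetic error.

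What is left is an undisclosed variability assumption. It would matter to someone sizing a trial from the 0.34 row, but this pilot is fixed at 10 participants, its anticipated VDP effect is the 1.02 row, and no enrolment, analysis or stated result changes. The conclusion rests on the paired t-test as a stand-in for the permutation test and on back-solved SDs. The mean-dependent variance is a plausible reading that the plan does not document, but the agreement between the 60% and its own row does not depend on it.

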Potential participants will be pre-screened for eligibility by trained research assistants via telephone. A verbal consent script will be used and an information sheet will be provided. Participants found to be eligible on pre-screening will be referred for the first study visit for full written informed consent for study procedures and for additional screening (See **Figure 1**, “Consent/Screen”). Screening forms for those who are found to be ineligible (or for those who are pre-screened as eligible but do not, for any reason, sign written informed consent at the first study visit) will be abstracted, reviewed by the PI, and then discarded in a secure fashion such that no PHI is retained.

First Study Visit

All eligible participants will undergo written informed consent, additional screening procedures, and initial evaluation and then be entered into a run-in period to ensure their ability to abstain from non-study e-cigarettes and regular cigarettes for the duration of the study (**Figure 1**).

Randomization

Participants who are confirmed as adherent after the run-in period will be immediately assigned by random number generator in SAS to receive the e-cigarette exposure on days 2-3 or on days

6-7, with a 72-hour period between exposed and unexposed conditions. Allocation will be concealed until Day 2, when the first experimental exposure is administered.

Experimental exposure

For the experimental exposure, all participants will use identical, study-provided e-cigarette devices; however, these study devices will not be shared between participants. Each device will be labeled with the participant number and stored securely between participant uses. After a participant completes the study, that participant's dedicated device will be discarded by Environmental Health and Safety.

"Pen-style" e-cigarettes confirmed to be MRI-safe will be used. Cartomizers, batteries, and e-liquids will be obtained from commercial suppliers. The e-cigarette device will be loaded with 2 mL of flavorless e-liquid with a ratio of PG to vegetable glycerin of 70:30 and 1.8 mg/dL of nicotine. Please see **Section 5.3** for additional product details.

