Participants will be asked to abstain from all tobacco products, with the exception of the study e-cigarette, from the first until the final study visit (11 days). Of note, tobacco product use will not be proscribed during the interval between the pre-screening telephone call and the first study visit.

4. **Results Reports:** No clinical reports will be generated for participants; however, a safety read will be performed as per CUMC policy.

5. **Study Drugs or Devices:**

- (1) **Hyperpolarized helium.** IND 123,115 has been obtained from the FDA. The helium gas is supplied by Linde Healthcare, [name] Phone: Main [contact]. The helium is hyperpolarized using the GE polarizer and administered by inhalation, as described in the IND application. There will be no charge to participants.
- (2) **Dotarem (gadoterate meglumine)** will be used as the contrast agent for the Gd-MRA at a low dose of 0.03 mmol/kg bodyweight. It will be supplied by Guerbet, [name]. Contacts include Toll Free: [contact]; [contact]; [contact].
- (3) **E-cigarette**
 - o Planned e-cigarette device: We will obtain e-cigarettes from KangerTech ([name]; [contact]). The model will be the Kanger Top Evod.
 - Alternate E-cigarette: If e-cigarette #1 is unavailable or there are other logistical issues identified, our alternate (highly similar) product will be from Halo (Corporate: [name]; Manufacturing: [name]; Customer Service: [contact]). We will use the "Triton" Variable Voltage Battery (adjustable voltage 3.3-4.8V, 900mAh, 10 seconds battery cut off time) "Triton" tank with 3.0-3.2 ohm coil.
 - o Study e-liquids: study e-cigarettes will be loaded with 2mL of flavorless e-liquid with a ratio of PG to vegetable glycerin (VG) of 70:30 and 1.8 mg/dL of nicotine (AVAIL Vapor, [name], contact [name] [contact]).

6. **Study Questionnaires:** See attached.

7. Study Subjects:

Inclusion criteria: Age of 21-35 years at time of enrollment and self-reported voluntary, recreational e-cigarette use (>1x/month but <daily).

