Exclusion criteria: any chronic major medical or psychiatric problems including current asthma; self-reported heavy snoring/sleep apnea; pre-bronchodilator FEV₁ or FVC <80% predicted or FEV₁/FVC < lower limit of normal⁵⁸; MRI exclusions (pregnancy, claustrophobia, metal in body, gadolinium allergy, eGFR <60 mL/min/1.73m²); MRI scan with contrast within the last 12 months or planned MRI with contrast in the next 6 months; use of any of the following in the prior 30 days: any conventional cigarettes, marijuana >10 days, any other illicit drugs, any daily medication (including inhalers) except hormonal contraceptives. Persons with an adverse symptomatic response to the study e-cigarette exposure (e.g., palpitations, shortness of breath, chest pain, headache, dizziness) will also be excluded.

8. Recruitment

Participants will be recruited from the local community and universities via fliers and word of mouth. There will be partial co-recruitment with the PI's related e-cigarette pilot studies AAAQ9965 and AAAR2000. Healthy volunteers may be drawn from CUMC/NYP personnel including residents/fellows/interns/staff. This latter recruitment will not be coercive as it is 100% voluntary and there is no recrimination for non-participation. CUMC/NYP personnel who report directly to the PI or co-I will not be recruited.

9. Informed consent and eligibility

Since the exclusion criteria for the VAPE-Tox Study are few but cannot be fully determined prior to the first study visit (Day -3), the participant will come into the clinic and first sign the informed consent and HIPAA forms. Participants will be invited to the Clinical and Translational Science Awards (CTSA) research suite, where they will be confirmed to meet all inclusion/exclusion criteria via questionnaires, exhaled CO (exCO), pre-bronchodilator spirometry, serum creatinine assay, urine pregnancy test for women, and a practice session for the study e-cigarette exposure under observation by a trained research assistant, before being asked to abstain completely from non-study e-cigarette use for the duration of the study. Eligibility will be confirmed by the PI in writing.

Adherent participants, defined on Day 0 as no interim self-reported e-cigarette use, ≤10 ppm exhaled CO (exCO), and urine cotinine (uCot) <100 ng/mL, will continue immediately with randomization.

10. Confidentiality of Study Data

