- a. **Nicotine exposure:** Side effects from products that contain nicotine can include sweating, lightheadedness, dizziness, nausea, and nervousness. These effects are unlikely in individuals who use nicotine-containing products regularly, but are more likely to occur in non-regular users. Regardless, these effects are transient and long-term adverse effects are not expected based upon the study exposure. Nicotine is also an addictive substance, therefore exposure to nicotine theoretically carries a risk of promoting addition; however, in the amounts and manner administered in the study, this is very unlikely to occur.
 - b. **Propylene glycol exposure:** propylene glycol is contained in most e-cigarette liquids, and will make up 70% of the study e-cigarette liquid. It is often used to make "theater fog" and is considered relatively safe, but it has occasionally been associated with shortness of breath or bronchospasm, especially in people with a history of asthma.
 - c. **Unknown risks:** The effects of e-cigarette use remain mostly unknown, which is the major motivation for this study. We are only recruiting young, healthy, adults who have already made the decision to use e-cigarettes intermittently, despite this uncertainty. A safety board will be monitoring the study.
2. **Claustrophobia:** A minority of individuals may be subject to psychological risks if they develop previously unknown claustrophobia inside the magnet. Claustrophobic episodes can be psychologically traumatic to participants; however, the trauma ceases upon removal of the subject from the scanner and does not have any known lasting effects.
 3. **Magnet risks:** All MRI studies involve exposure to magnetic field strength, rate of change of magnetic field gradients, and RF power exposure within guidelines recommended by the Food and Drug Administration.
 4. Risks relating to **gadolinium contrast:**
 - a. **Nephrogenic Systemic Fibrosis (NSF)** is a rare fibrosing condition of the skin and organs that has been reported in association with gadolinium contrast agents and severe renal failure (GRF < 30 ml/min/1.73 m²). No reported cases have occurred above this level in patients with chronic renal impairment. Acute onset renal failure, hepatorenal syndrome, peri-hepatic transplant or kidney transplant represent additional risk factors. The clinical course of NSF is progressive and

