2. **Questionnaires:** There is minimal risk related to questionnaires, this involves the social-psychological risk from the inadvertent disclosure of confidential medical information. We guard against this by maintaining study information identified by study number only in a filing system separate from the name and address files.
3. **Phlebotomy:** The risks associated with blood collection are minimal and include the potential to feel a little pain or get a bruise at the place where the blood is drawn. It is possible, but not likely, that there may be swelling or bleeding at the site.
4. **EBC** testing is non-invasive and involves minimal risks.
5. **Spirometry:** Spirometry is non-invasive and involves minimal risks. Spirometry can induce shortness of breath, coughing or chest tightness, and may cause the participant to feel lightheaded. It is very rarely complicated by syncope. No bronchodilators will be administered.

6. **E-cigarette exposure:** We will only recruit young, healthy, current e-cigarette using adults. Since these subjects choose to use e-cigarettes recreationally, it is reasonable to infer that they have determined independently that they are willing to accept the mostly unknown risks associated with e-cigarette vapor. Nonetheless, we will mitigate any potential risks associated with the standardized study exposure – which will employ short-term exposure to publicly available e-cigarette products containing a standardized e-liquid with moderate nicotine content and without flavorings – by requiring a monitored “test run” of the study e-cigarette exposure at the enrollment visit. All persons with an adverse response (e.g., palpitations, shortness of breath, chest pain, headache, dizziness) will be excluded. We will also provide symptomatic and hemodynamic monitoring throughout the study procedures.
7. **Claustrophobia:** We include severe, known claustrophobia as a contraindication to participation in this project
8. **Magnet risks:** All subjects will be screened to exclude those with contraindications to MR, including those with pacemakers, aneurysm clips, cochlear implants or other implanted electronic devices. Subjects with a history of occupational exposure to small metallic projectiles will also be excluded. The MR scanner areas at the sites are equipped with standard medical emergency equipment for a hospital-based MR center.
9. **Gadolinium contrast:**

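### Eligibility does not require nicotine use, so people who vape only nicotine-free liquid can enroll, receive nicotine three times, and have their run-in abstinence checked by self-report alone

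*Combined protocol and SAP*

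**What the plan says.** **Who may enter.** Section 7 asks for age 21 to 35 and "self-reported voluntary, recreational e-cigarette use (>1x/month but <daily". The exclusions on prior use cover "use of any of the following in the prior 30 days: any conventional cigarettes, marijuana >10 days, any other illicit drugs", plus daily medication. Neither list refers to the nicotine content of the person's usual product.

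**What they receive.** Under Experimental exposure in section 2, every device is "loaded with 2 mL of flavorless e-liquid with a ratio of PG to vegetable glycerin of 70:30 and 1.8 mg/dL of nicotine". Section 3, item 9, schedules the exposure at the enrollment visit and at two of the four imaging visits. Of the 10-puff exposure the plan says: "This is anticipated to generate a plasma nicotine concentration of 19 ng/mL, similar to 10 puffs of a conventional cigarette".

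**How abstinence is checked.** Section 9 defines adherence on Day 0 as "no interim self-reported e-cigarette use, ≤10 ppm exhaled CO (exCO), and urine cotinine (uCot) <100 ng/mL". Section 3, item 5, describes exhaled CO as a sign of recent conventional smoking.

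**How the exposure is justified.** Section 11, item 1a, says of nicotine side effects: "These effects are unlikely in individuals who use nicotine-containing products regularly, but are more likely to occur in non-regular users". Section 12, item 6, argues: "Since these subjects choose to use e-cigarettes recreationally, it is reasonable to infer" that they accept the largely unknown risks of the vapor. The same item requires a monitored trial of the exposure at enrollment and excludes anyone who reacts badly to it.

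**The concern.** The plan knows that e-cigarettes come with and without nicotine. Section 1 says both kinds of vapor impair the endothelial barrier in vitro, and later studies are to vary nicotine content. The entry criterion does not carry this distinction through, which leaves two gaps for a participant who uses only nicotine-free liquid.

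The first is participant protection. The plan treats existing e-cigarette use as evidence that the person has accepted the exposure. Nicotine is listed as a separate risk, with its own side effects and a stated, if very unlikely, potential for addiction. A nicotine-free user has not chosen it.

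The second is the run-in, whose stated purpose is to make sure participants can stay off non-study e-cigarettes and cigarettes. For this person the laboratory part of the check does not address the product they actually use. Section 1 names heated propylene glycol as an airway irritant and nicotine-free vapor as active on endothelium, so unnoticed vaping could bear on both imaging measures. With 10 participants, one person is a tenth of the data.

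**Working it through.** The plan gives no figure on this point, so the main check sets its sections against each other for one hypothetical candidate: aged 21 to 35, healthy, vaping only nicotine-free liquid twice a month, no cigarette in the past 30 days.

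1. **Eligibility (section 7).** Twice a month is more than monthly and less than daily, so the use criterion is met. No exclusion concerns nicotine experience. The candidate is eligible as written.

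2. **Nicotine received (section 3, item 9).** 1 exposure at enrollment + 2 at imaging visits = 3. The first is the practice session, used to confirm eligibility under section 9, so it takes place before a poor response can exclude anyone.

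3. **Day 0 check (section 9), part by part, for continued nicotine-free vaping:**

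| Part | Can it register this vaping? |
|---|---|
| Self-report of no interim e-cigarette use | Yes, if the person reports it |
| Exhaled CO ≤10 ppm | Not its described purpose (section 3, item 5: conventional cigarettes) |
| Urine cotinine <100 ng/mL | No; cotinine is a breakdown product of nicotine, so nicotine-free liquid yields none |

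 Only self-report remains. Any cotinine found in this person on Day 0 may also come from the study's own enrollment exposure.

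4. **Risk rationale (sections 11 and 12).** Section 11 ties a low chance of side effects to regular use of nicotine-containing products. Section 12 ties acceptance of risk to recreational use of e-cigarettes. The candidate satisfies the second condition and not the first.

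5. **Chance of enrolling such a person.** The documents give no share of nicotine-free users, so p is an assumption. With 10 independent participants, P(at least one) = 1 − (1 − p)^10:

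| Assumed p | Calculation | Result |
|---|---|---|
| 5% | 1 − 0.95^10 | 40% |
| 10% | 1 − 0.90^10 | 65% |
| 20% | 1 − 0.80^10 | 89% |
| 40% | 1 − 0.60^10 | 99% |

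6. **What that figure does not measure.** Undetected vaping also requires the person to vape and to deny it. If, purely for illustration, p = 10% and 20% of such users did so, the per-person probability would be 0.10 × 0.20 = 0.02, and the chance of at least one among 10 would be 1 − 0.98^10 = 18%, not 65%.

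**The case against.** The opposing case is strong on consequences.

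- **Self-report is a check.** The Day 0 rule asks about e-cigarette use of any kind. A breach goes unseen only if the person both vapes and denies it. This stands: the check is weaker for nicotine-free users but not absent.
- **Bias is not shown.** A reader might infer that undetected vaping biases the comparison toward no effect. The documents do not support that. Each participant is their own control for an acute, directly observed exposure, and off-protocol vaping could precede scans in either condition. It could add noise or, if it fell before unexposed scans, attenuate the contrast. Neither can be sized from the plan.
- **Safeguards exist.** The monitored trial at enrollment, exclusion of symptomatic responders, hemodynamic monitoring and a DSMB all apply, and section 11 calls the side effects transient and addiction very unlikely. This stands in part. The trial run is itself a nicotine exposure and has no bearing on abstinence from the usual product.
- **The remedy is incomplete.** People who use both kinds of liquid could still vape the nicotine-free kind unseen by cotinine, and someone who vapes nicotine twice a month is hardly a regular user either. This stands and limits what can be claimed for the change.
- **The question may already be asked.** The 18-question telephone screen and the e-cigarette questionnaires are attachments not in the text supplied. They may record nicotine content. Even so, section 3 describes the telephone screen as covering the entry criteria, and those contain no nicotine requirement to apply.
- **Breadth is a legitimate choice in a pilot.** True, but the plan does not say that nicotine-free users are wanted.

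**Conclusion.** The point holds as a modest, inexpensive gap in eligibility. As written, the plan admits people who use only nicotine-free liquid, gives them nicotine on three scheduled occasions under a rationale that does not cover nicotine, and leaves their run-in abstinence to self-report. This follows from the text and from one premise that the plan does not spell out, namely that cotinine reflects nicotine intake.

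The likelihood is unknown. The 40% to 99% range is the chance of enrolling at least one such person under assumed shares of 5% to 40%, and nothing more. A reader might take it as the chance of a contaminated result, or conclude that the run-in fails outright; the documents support neither. No stated figure in the plan is shown to be wrong by this point.

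**What to change.** In section 7, reword the use criterion to self-reported voluntary, recreational use of nicotine-containing e-cigarettes, keeping the existing frequency limits. Confirm the nicotine content of the usual e-liquid in the telephone pre-screen and again at Day -3, unless the attached questionnaires already do this.

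In section 9, add a sentence acknowledging that abstinence from nicotine-free liquid, including by participants who use both kinds, rests on self-report because cotinine cannot show it.

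The change removes the group for whom cotinine says nothing about the usual product and for whom the risk-acceptance argument does not reach nicotine. It does not make cotinine sensitive to nicotine-free vaping by others, nor does it make nicotine tolerance uniform among intermittent users. If the sponsor does want nicotine-free users, the protocol should say so and extend the risk rationale to them.

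Cost: one phrase, one sentence, at most one screening question asked twice, and a slightly smaller recruitment pool.
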